02 OCT 2017

[figure not shown]
Date

Chief Medical Officer
Medicines360

02 October 2017

Date

Vice President of Quality Assurance
Medicines360

03 Oct 2017

Date

Biostatistics

02 October 2017

Date

PROTOCOL SYNOPSIS

Study Title	A Phase 3, Multi-Center, Open-Label Study of a Levonorgestrel-Releasing Intrauterine System for Long-Term, Reversible Contraception
Short Title	LNG20 IUS Phase 3 study for contraception
Study Sponsor	Medicines360
Protocol Number	M360-L102
Study Phase	3
Study Objectives	
The primary objective of this study is to assess the efficacy of a levonorgestrel-releasing intrauterine system (LNG20) in nulliparous and parous females of child-bearing potential who request long-term, reversible contraception.
 
The secondary objectives of this study are to assess:
 
• safety, tolerability, bleeding patterns, and continuation rates of LNG20• return of menses after discontinuation of LNG20• return to fertility after discontinuation of LNG20• plasma pharmacokinetics of levonorgestrel in a subset of approximately 60 subjects with serial sampling over the duration of use• plasma levonorgestrel levels in subjects with continuing use from Month 36 through Month 120• levonorgestrel levels over the first 14 days following removal in a subset of 60 subjects using the LNG20 and completing the entire duration of use• changes in endometrial thickness in a subset of 60 subjects based on transvaginal ultrasonography at 1, 5 and 10 years of LNG20 use• safety and tolerability of LNG20 in a small cohort of women between ages 36 and 45 years for up to 8 years duration of use• analysis of an appropriate sampling of IUSs that are removed and, when available, expelled during the study

Planned Study Dates	Start of study/recruitment: November 2009 End of recruitment: April 2013 End of study treatment: May 2023 End of post-treatment follow-up: May 2024
Number of Investigative Sites	Up to 30 sites in the U.S.
Number of Subjects Planned	Approximately 1,910 women between the ages of 16 and 45 years, inclusive, who request long-term, reversible contraception, provide consent, and satisfy study entry criteria will be enrolled. The sample will include: 
• approximately 1,760 women between 16 and 35 years of age, inclusive, at enrollment• approximately 150 women between 36 and 45 years of age, inclusive, at enrollment
Study Design	The primary study is a randomized, multi-center, open-label, evaluation of the efficacy of a levonorgestrel-releasing intrauterine system (LNG20). A marketed levonorgestrel-releasing intrauterine system (Mirena®) is included as an informative comparator. Eligible subjects 16-35 years of age will include approximately 1,600 subjects using LNG20 and 160 subjects using Mirena. Approximately 650 LNG20 and 160 Mirena subjects were randomized at a 4:1 ratio of LNG20 to Mirena. However, the remaining 950 subjects will be assigned to LNG20 only. In addition, approximately 150 eligible females 36-45 years old will receive LNG20 as part of a non-randomized cohort. After consent is obtained, screening procedures will be performed and eligible subjects enrolled into the trial via an Interactive Voice Response System (IVRS). The Enrollment Visit and IUS insertion may occur on the same day as the screening procedures. The study IUS will be inserted by a study Investigator using a standardized insertion procedure. Subjects will be evaluated during study treatment use for up to 121 months (60

months for Mirena subjects and 96 months for the LNG20 36-45 year old enrollment group). Study assessments will be performed at a clinic visit at Months 1, 3, 6, 12, 18, 24, 30, 36, 42, 48, 54, 60, 66, 72, 78, 84, 90, 96, 102, 108, 114, 120 and 121 (Mirena subjects only through Month 60 and the LNG20 36-45 year old enrollment group only through Month 96). Telephone assessments will occur at 3 month intervals between scheduled clinic visits, starting at Month 9. The IUS will be removed when requested, when clinically indicated, or at the end of duration of use which is 121 months for LNG20 subjects, 60 months for Mirena subjects and 96 months for the LNG20 36-45 year old enrollment group.

All subjects will have a safety follow-up visit one month after discontinuing study treatment. Additional follow-up will be conducted for subjects who choose a non-hormonal contraceptive method or who indicate they will attempt to become pregnant, as follows:

- Those women who elect to start a non-hormonal contraceptive method or no contraception (including those desiring pregnancy) will be followed for return of menses
- Those women who desire pregnancy will be followed for up to 12 months following IUS removal or expulsion to document return to fertility

Pregnancies will be identified during treatment through subject query and urine pregnancy tests at each scheduled study visit, and after treatment discontinuation (1 month safety follow-up). The date of conception will be estimated by ultrasound examination for pregnancies that occur during study participation.

Routine safety monitoring (adverse event assessments and vital signs) will be conducted for all subjects. An Independent Data Monitoring Committee (IDMC) will monitor subject safety throughout study conduct, and will be sent reports of all unexpected related serious adverse events (SAEs) that may occur during the study. The IDMC will review all safety data and make recommendations regarding study conduct.

Subjects will receive detailed instructions on how to record vaginal bleeding, dysmenorrhea and other contraceptive use in a daily diary and report this information during the first 24 months of study participation. Thereafter, only other contraceptive use will continue to be recorded on a diary by the subject for the remainder of study participation in addition to the information collected at each study visit. After 24 months, bleeding and dysmenorrhea information only will be obtained for the remainder of study participation via interviews by study staff during each study contact (every 3 months) during treatment. Levonorgestrel plasma levels will be obtained for all subjects every 6 months and at IUS discontinuation beginning with Month 36 until Protocol Version 9 when thereafter, levonorgestrel plasma levels will be obtained in all subjects at IUS discontinuation and also annually in all women enrolled prior to 31 May 2011. The Sponsor intends to retain all IUSs that are removed or expelled (when available) and analyze an appropriate sample of these.

The following substudies for women 16-35 years will occur at selected sites:

- Levonorgestrel PK data will be generated in a subset of approximately 60 subjects, (20 non-obese LNG20 subjects, 20 non-obese Mirena subjects and 20 obese LNG20 subjects). Blood samples will be obtained at the Enrollment Visit (pre-IUS insertion), Weeks 1 and 2, and Months 1, 3, 6, 9, 12, 18, 24 and 30 after IUS insertion
- A subset of 60 women assigned to LNG20 will have transvaginal ultrasound evaluations at Enrollment, Month 12, Month 60 and Month 120 to assess endometrial thickness
- A subset of 60 subjects assigned to LNG20 and completing 121 months of study treatment will have levonorgestrel samples obtained at various timepoints after study IUS removal for the characterization of the elimination profile of LNG. Each subject in this subset will be randomized to one timepoint (one extra visit) post-IUS removal (24 hours, 48 hours, 7 days or 14 days) such that fifteen subjects are randomly assigned to each timepoint

Investigational Drugs:	A levonorgestrel-releasing intrauterine system (LNG20) with an initial release rate of approximately 20 mcg/day will be evaluated. A marketed levonorgestrel-releasing intrauterine system (Mirena) with an initial release rate of approximately 20 mcg/day will be included as an informative comparator.
Dosing Regimen:	At study entry, a LNG20 or Mirena will be inserted into the uterus by a study Investigator using standardized procedures specific to each system. The LNG20 will be removed at Month 121 for the 16-35 year old enrollment group and at Month 96 for the LNG20 36-45 year old enrollment group. Mirena will be removed at Month 60. Either IUS may be removed earlier if requested by the subject or judged necessary by the Investigator. Subjects who experience IUS expulsion (partial or complete) will be discontinued from study treatment. An IUS that is expelled during the study will not be replaced with a new LNG20 or Mirena IUS in this study.
Primary Outcome Measure:	Efficacy of LNG20 at 2 years of use. This outcome will be established in the Modified Intent To Treat (MITT) population by calculating the Pearl Indices for use during year 1 and year 2. The Pearl Index for each year must have acceptable precision, defined as the upper bound of the 95% confidence interval being no more than 1 unit above the point estimate.
Key Secondary Outcome Measures:	Efficacy of LNG20 at 3, 4, 5, 6, 7, 8, 9 and 10 years of use. This outcome will be established in the MITT population by calculating the Pearl Indices for use during year 3, year 4, year 5, year 6, year 7, year 8, year 9 and year 10.
Other Secondary Outcome Measures:	Other secondary outcomes that will be assessed for LNG20 and Mirena will include: 
• Cumulative LNG20 pregnancy rates for years 2 through 10• IUS continuation rates at 1 year, 2 years, 3 years, 4 years, 5 years, 6 years, 7 years, 8 years, 9 years, 10 years

- Years 6, 7 and 8 will only include LNG20 subjects
- Years 9 and 10 will only include the LNG20 16-35 year old enrollment group
- IUS expulsion rates at 1 year, 2 years, 3 years, 4 years, 5 years, 6 years, 7 years, 8 years, 9 years and 10 years
 - Years 6, 7 and 8 will only include LNG20 subjects
 - Years 9 and 10 will only include the LNG20 16-35 year old enrollment group
- IUS safety-related removal rates at 1 year, 2 years, 3 years, 4 years, 5 years, 6 years, 7 years, 8 years, 9 years and 10 years
 - Years 6, 7 and 8 will only include LNG20 subjects
 - Years 9 and 10 will only include the LNG20 16-35 year old enrollment group
- Vaginal bleeding patterns during IUS use
- Dysmenorrhea during IUS use
- Hemoglobin over the duration of IUS use
- Adverse events
- Pregnancy outcomes
- Fertility rates one year following removal of the IUS
- Occurrence of menses after IUS discontinuation
- Plasma levonorgestrel levels over the duration of IUS use
- Analysis of an appropriate sampling of IUSs that are removed or expelled during the study

Other secondary outcomes that will be assessed for LNG20 will include:

- Plasma levonorgestrel levels over the first 14 days following LNG20 removal after Month 121
- Endometrial thickness at 1, 5 and 10 years of LNG20 use as compared to baseline

Duration of Subject Participation:	LNG20 16-35 year old enrollment group: up to 11 years, 1 month (approximately 133 months) LNG20 36-45 year old enrollment group: up to 9 years, 1 month (approximately 109 months) Mirena group: up to 6 years, 1 month (approximately 73 months)
Duration of Study Center Participation:	Up to 14.7 years from start of study enrollment assuming 3 months for study start-up activities, an enrollment period up to 3 years, up to 10 years and 1 month subject treatment, 1 year pregnancy follow-up and 3 months post-monitoring/query resolution.
Eligibility Criteria:	Inclusion Criteria Subjects must fulfill all of the following criteria to be eligible for study entry: 
1) Signed informed consent2) Healthy females 16-45 years of age, inclusive, at the time of enrollment (unemancipated subjects less than 18 years of age must also have written parental consent documented on the consent form)3) Regularly sexually active and in a mutually monogamous relationship for at least 6 months at study entry4) Willing to rely on the study IUS as the primary method of contraception during study participation5) History of regular menstrual cycles defined as occurring every 21-35 days when not using hormones and with a variation of typical cycle length of no more than 5 days6) Willing to comply with study visit schedule and assessments, including diary completion requirements7) Planning to reside within a reasonable driving distance of a study research site (approximately 150 miles) for at least 2 years

Exclusion Criteria

Subjects meeting any of the following criteria will be ineligible for study entry:

- 1) Currently pregnant
- 2) Pregnant within 4 weeks prior to study entry
- 3) Planning pregnancy within 24 months of study entry
- 4) Currently breastfeeding
- 5) History of ectopic pregnancy without a subsequent intrauterine pregnancy
- 6) History of trophoblastic disease (benign or malignant gestational) without a subsequent non-trophoblastic intrauterine pregnancy
- 7) Acute pelvic inflammatory disease or a history of pelvic inflammatory disease without subsequent intrauterine pregnancy
- 8) History of a positive HIV test or having a partner who is known to be HIV positive
- 9) History of cervical or vaginal infection (unless successfully treated and considered clinically cured for at least 7 days prior to study entry)
- 10) Postpartum or post-abortion endometritis unless symptoms resolved at least 4 weeks prior to study entry
- 11) Current persistent, abnormal vaginal bleeding
- 12) Abnormal Pap test based on the following criteria:
 - Pap test in the past 18 months with ASC-US unless:
 - less than 21 years of age;
 - a repeat Pap test at least 6 months later was normal;
 - reflex HPV testing was performed and was negative for high-risk HPV; or
 - a colposcopy (with or without biopsy) found no evidence of dysplasia requiring treatment or treatment was performed and

follow-up at least 6 months after the treatment showed no evidence of disease

- Pap test in the past 18 months with LSIL unless:
 - less than 21 years of age; or
 - a colposcopy (with or without biopsy) found no evidence of dysplasia requiring treatment or treatment was performed and follow-up at least 6 months after the treatment showed no evidence of disease
- Pap test in the past 18 months with ASC-H, atypical glandular cells, or HSIL unless colposcopy and/or treatment was performed and follow-up at least 6 months after the colposcopy and/or treatment showed no evidence of disease
- Pap test in the past 18 months with malignant cells
- Pap test more than 18 months ago that was abnormal without any appropriate follow-up evaluation

13) History of malignancy of the genital tract (e.g. cervical cancer, ovarian cancer, endometrial cancer)

14) History of breast cancer, or suspicion of breast cancer until proven otherwise

15) History of bicornuate uterus or any other abnormality of the uterus resulting in distortion of the uterine cavity or cervical canal incompatible with insertion

16) Known or suspected allergy to levonorgestrel or hypersensitivity to any component of the product

17) Bleeding diathesis (inherited or acquired)

18) Use of anticoagulants within 30 days prior to study entry

19) Body habitus, or history of lower genital tract abnormalities or prior surgeries which may prohibit proper visualization of the cervix or not allow the uterus to be appropriately instrumented [Note: any woman

	
who may meet this criteria should have a pelvic examination prior to randomization to confirm that the cervix cannot be properly visualized for IUS insertion]
 
20) Current or history of alcohol, or illicit or prescription drug abuse within 12 months prior to study entry
 
21) Current use of hormonal contraception for cycle control
 
22) DMPA (Depo-Provera®/Depo-Ralovera®) injection within the past 9 months (this exclusionary time period can be shortened to 6 months if the subject has also had two spontaneous menstrual cycles [requires minimum of 3 menses] that meet criteria for normal menstrual cycles)
 
23) Current use of non-contraceptive estrogen, progesterone, testosterone, or other gonadotropins (e.g. hCG)
 
24) Use of an experimental medication or receipt of an experimental treatment for any condition within 30 days of study entry
 
25) Study staff or a member of the immediate family of a study staff
 
26) Any condition or circumstance that, in the opinion of the Investigator, would constitute contraindications to participation in the study or would compromise ability to comply with the study protocol, such as any concurrent medical condition that is not stable and well-controlled, that is likely to worsen, or that may require recurrent hospitalizations during study participation
 
27) History of bipolar disorder, schizophrenia, psychosis, major depressive disorder or other major psychiatric disorder according the criteria of the Diagnostic and Statistical Manual of Mental Disorders, Fourth Edition (DSM-IV-TR)

Statistical Methods:	The following analysis populations will be created: 
• Safety (Safety): All subjects enrolled who underwent the IUS insertion procedure, regardless of age and outcome.

- Modified Intent To Treat (MITT): All LNG20 subjects between 16 and 35 years of age at study entry for whom the assigned IUS is successfully placed in the uterus and for whom there is at least one report of pregnancy status after inserting the IUS.
- Per Protocol (PP): A subset of the MITT population that excludes subjects with major protocol deviations (to be identified prior to data lock).

The Pearl Index with 95% confidence interval for women in the MITT population will be used to establish efficacy for 2 years of use. Cycles (defined as 28 days) during which backup methods of contraception are used will be excluded from the primary analysis of the Pearl Index unless the subject became pregnant in that cycle. Pregnancies judged to have occurred while a study IUS was in place and up to and including 7 days after IUS discontinuation (determined by ultrasound and medical assessment) will be included in these calculations. To establish the efficacy of LNG20 for 2 years of use, acceptable precision of the Pearl Index must be reached during year 1 and, separately, during year 2, where acceptable precision is defined as the upper bound of the 95% confidence interval being no more than 1 unit above the point estimate of the Pearl Index.

Secondarily the Pearl Index will be calculated for use during years 3, 4, 5, 6, 7, 8, 9 and 10.

The Mirena arm of approximately 160 subjects is included as an informative comparator only.

All other secondary endpoint analyses will be descriptive.

Vaginal bleeding patterns (none, spotting, and light, normal, or heavy flow) and dysmenorrhea (none, mild, moderate, or severe) will each be summarized by the percentage of days with a particular pattern during each 90 day intervals after enrollment.

All treatment emergent adverse event data will be presented by MedDRA system organ class, preferred term and treatment group. Quantitative safety

	variables (e.g., vital signs) will be summarized at each visit by treatment group in addition to changes from baseline. Analysis of a sampling of retained IUSs will be summarized. Levonorgestrel plasma levels will be obtained for all subjects every 6 months and at any IUS discontinuation visit beginning with Month 36 until Protocol Version 9 when thereafter, levonorgestrel plasma levels will be obtained in all subjects at IUS discontinuation and also annually in all women enrolled prior to 31May2011.
Sample Size:	Approximately 1,910 women will be enrolled into the study. Approximately 1,760 women will be assigned to LNG20 or Mirena, with the goal that a minimum of approximately 1,600 LNG20 and 160 Mirena users are enrolled between the ages of 16 and 35 years. Another 150 women 36-45 years of age will be enrolled in a non-randomized cohort and receive LNG20. It is expected that 1,600 LNG20 subjects between the ages of 16 and 35 years will provide at least 10,000 woman-months of exposure in the first two years and at least 360 woman-years of use in the final year of the study for the LNG20.

TABLE OF CONTENTS

TITLE PAGE	1
SIGNATURE PAGE	2
PROTOCOL SYNOPSIS	3
TABLE OF CONTENTS.....	15
ABBREVIATIONS AND DEFINITIONS.....	20
1. INTRODUCTION	22
1.1 Current Intrauterine Contraception Options	22
1.1.1 History and Clinical Experience to Date	22
1.2 Medicines360 Levonorgestrel-Releasing Intrauterine System	24
2. STUDY OBJECTIVES.....	25
2.1 Primary Objective	25
2.2 Secondary Objectives.....	26
3. INVESTIGATIONAL PLAN.....	26
3.1 Study Design and Plan.....	26
3.2 Outcome Measures.....	29
3.2.1 Primary Outcome Measure	29
3.2.2 Key Secondary Outcome Measures	29
3.2.3 Other Secondary Outcome Measures.....	30
4. STUDY POPULATION SELECTION	31
4.1 Subject Selection.....	31
4.2 Inclusion Criteria	31
4.3 Exclusion Criteria	32
4.4 Substudies Entry Criteria	34
4.4.1 Treatment PK Substudy	34
4.4.2 Endometrial Thickness Substudy.....	35
4.4.3 Elimination PK Substudy.....	35
5. STUDY TREATMENTS	35

5.1	LNG20 IUS (Dosage and Formulation).....	36
5.2	Mirena IUS (Dosage and Formulation)	36
5.3	IUS Supply and Administration.....	36
5.4	IUS Storage and Accountability	36
5.5	IUS Replacement	37
5.6	Concomitant and Excluded Therapy.....	37
5.7	Blinding.....	38
6.	STUDY PROCEDURES	38
6.1	Clinical Laboratory Tests.....	38
6.2	IUS Insertion Definitions.....	38
6.3	Screening/Enrollment Visit.....	39
6.3.1	Screening Procedures.....	40
6.3.2	Enrollment Visit Procedures	41
6.4	Post-Insertion Study Follow-Up Visits.....	43
6.5	Contacts Between Study Visits.....	46
6.6	Study Treatment Completion/Early Discontinuation.....	47
6.7	30-Day Safety Follow-Up.....	48
6.8	Unscheduled Visits	50
6.9	Diagnostic Ultrasound Examinations	50
6.10	Substudy Procedures	50
6.10.1	Treatment PK Substudy	50
6.10.2	Endometrial Thickness Substudy.....	51
6.10.3	Elimination PK Substudy.....	51
6.11	Pap Testing.....	51
6.12	Management of Abnormal Testing During the Study.....	53

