4.4 Substudies Entry Criteria

4.4.1 Treatment PK Substudy

In addition to meeting all entry criteria for the primary study, subjects desiring to enter the PK substudy must meet all of the following criteria:

- be 16-35 years old at the time of enrollment in the primary study

- have signed informed consent for the PK sampling prior to collection of the blood sample on day of IUS insertion
- have venous access adequate for multiple blood draws
- have not received hormonal contraception within 7 days of enrollment

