4.4.2 Endometrial Thickness Substudy

In addition to meeting all entry criteria for the primary study, subjects desiring to enter the substudy assessing endometrial thickness must:

- be 16-35 years old at the time of enrollment in the primary study
- be assigned to LNG20
- have signed informed consent for the endometrial thickness assessments prior to IUS assignment

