6.3 Screening/Enrollment Visit

Screening is considered to start with the signing of the Informed Consent Form by the subject. Although the Screening and Enrollment Visits may occur during one visit, the Screening procedures may be performed over multiple days. The Enrollment Visit is considered to be on the date the subject is assigned through the IVRS. Screening test results are not required to be available prior to the Enrollment Visit.

Scheduling of the Enrollment Visit must take the following schemes into account:

- When switching from an oral, transdermal or vaginal hormonal contraceptive, the subject should continue that method after the study IUS insertion until the end of the current cycle. If using the contraceptive continuously (without a hormone free interval), then discontinue 7 days after IUS insertion. When possible, the Enrollment Visit should be scheduled during the hormone-free time of the cycle (i.e., “placebo week,” “patch-free week,” or “ring-free week”)
- When switching from an injectable monthly combined hormonal injection, the study IUS insertion may occur anytime within 28 days of the last injection
- When switching from non-hormonal contraception (except copper IUD), the study IUS insertion **must** be performed within the first 7 days of the menstrual cycle

- When switching from a contraceptive implant, another hormonal IUS, or a copper IUD, the study IUS insertion may occur anytime in the menstrual cycle but should occur on the same day as removal of the implant, non-study IUS, or IUD
- Women who need a screening Pap test (see section 6.11) should be scheduled for screening on a day they are expected to have minimal or no bleeding
- All enrollment procedures must be completed within 30 days of screening. If greater than thirty days, Medical Monitor approval must be obtained before rescreening or enrollment

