6.3.2 Enrollment Visit Procedures

Once the IVRS is contacted and an IUS is assigned, the subject is considered enrolled. Insertion of the assigned IUS must be attempted on the same day the IVRS assignment occurs. Second insertion attempts are allowed and can occur on a different day, but must be within 30 days of signing the informed consent. The day of successful IUS insertion is considered Study Day 1. Enrollment procedures and study IUS insertion must be scheduled per the guidelines outlined in Section 6.3. If screening and enrollment are occurring on the same day, all screening laboratory blood or urine testing must be collected prior to enrollment in the IVRS; cervical tests may be collected at the time of insertion.

- For women having enrollment on the same day as screening:
 - Perform all screening procedures prior to contacting the IVRS except for the pelvic exam and any cervical testing which can be performed as a continuum with the insertion procedure *EXCEPTION:* a separate pelvic exam must be completed prior to contacting the IVRS if there is clinical suspicion that anatomical issues may prevent successful insertion
- For women having enrollment on a different day than screening, include the following:
 - Repeat a high sensitivity urine pregnancy test prior to calling the IVRS
 - Review results of screening tests, if available:
 - If screening test results **are not** available prior to enrollment

- Enrollment may proceed **unless** an entry criteria Pap test result is pending (See section 6.11)
- If screening test results **are** available prior to enrollment:
 - If a Pap test was performed and meets the exclusion criteria, the subject must not be enrolled; however, she can be re-screened if entry criteria are satisfied at a future date
 - If STD testing (Chlamydia or gonorrhea) is positive, enrollment must be delayed until the subject completes appropriate antibiotic treatment
 - If tests are appropriately collected but reported unevaluable prior to enrollment or successful insertion the tests must be repeated
- Enrollment procedures:
 - Confirm eligibility criteria
 - Enroll in IVRS
 - Insert IVRS assigned study IUS using the techniques described in the Investigator's Brochure.
 - Up to two attempts for insertion can be made. Each attempt should use a new IUS of the assigned treatment group. The IVRS must be contacted before each attempt
 - If the IUS is unable to be inserted after two attempts or the uterus sounds to <5.5 cm:

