6.10.2 Endometrial Thickness Substudy

Subjects in this substudy will be assigned the LNG20. Endometrial thickness assessments will be made at Enrollment (pre-IUS insertion), Month 12, Month 60 and Month 120 study visits. The assessment at Enrollment should occur after IVRS assignment to LNG20 and before IUS insertion. If IUS removal is planned at the same study visit, the endometrial thickness assessment should occur before IUS removal. Endometrial thickness should not be assessed at any other visits, including an early Discontinuation Visit (unless that visit is occurring at Month 12, Month 60 or Month 120). Endometrial thickness is defined as the maximal dimension of the endometrial cavity in the anterior-posterior plane of the uterus, including all contents of the endometrial cavity, and will be measured in a longitudinal view of the uterine cavity using transvaginal sonography.

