11.14 Endometrial Thickness

Endometrial thickness at baseline and after 1, 5 and 10 years of LNG20 use will be summarized using the ET population. Changes from baseline will also be summarized. Baseline is defined as the last non-missing value prior IUS insertion.

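### The baseline endometrial scan may be taken in women still on, or that day coming off, a hormonal contraceptive, and the SAP pools change from baseline without separating them

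*Protocol*

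**What the plan says.** The outcome, as listed in the protocol synopsis, is "Endometrial thickness at 1, 5 and 10 years of LNG20 use as compared to baseline". The synopsis promises "A subset of 60 women assigned to LNG20 will have transvaginal ultrasound evaluations", at enrollment and Months 12, 60 and 120. The substudy has no comparator arm, so baseline is the only reference.

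- **Timing of the baseline scan.** Protocol 6.10.2: "The assessment at Enrollment should occur after IVRS assignment to LNG20 and before IUS insertion". Protocol 6.3.2: "Insertion of the assigned IUS must be attempted on the same day the IVRS assignment occurs".
- **Switching rules (Protocol 6.3).** For a woman on a pill, patch or ring, "the subject should continue that method after the study IUS insertion until the end of the current cycle". A woman on a monthly combined injection may be inserted up to 28 days after the last dose. Implant, hormonal-IUS and copper-IUD users should switch on the day of removal. Other non-hormonal users are inserted in the first week of the cycle.
- **Entry to the endometrial substudy (Protocol 4.4.2).** The list opens "In addition to meeting all entry criteria for the primary study, subjects desiring to enter the substudy assessing endometrial thickness must" and then asks only for age 16 to 35, assignment to LNG20 and consent.
- **Entry to the Treatment PK substudy (Protocol 4.4.1).** Here women must "have not received hormonal contraception within 7 days of enrollment".
- **Analysis (SAP 6 and 11.14).** The population is everyone in the substudy with at least one post-insertion measurement. Baseline is the last value before insertion. Thickness is summarized at each time, and "Changes from baseline will also be summarized". Prior method is not among the subgroups in SAP 5.9.

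**The concern.** A change-from-baseline summary in a single group is only as clear as its baseline. If some women are scanned with a hormonal method on board and others without, the pooled mean averages two quantities: change from an untreated endometrium, and change from one that may already be under a progestin or a combined hormonal method.

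The sharpest case can be made from the protocol alone. Sections 5.1 and 5.2 give both LNG20 and Mirena 52 mg of levonorgestrel. For a woman who has a Mirena removed and LNG20 inserted on the same day, change from baseline compares one such system with another.

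The plan takes care over this elsewhere. Protocol 9.8 records baseline bleeding and baseline dysmenorrhea as they were off hormonal contraception. Endometrial thickness has no equivalent. SAP 10.3.2 also plans exposure-response analyses that include endometrial thickness, so a mixed baseline could carry into those.

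**Working it through.** The documents give no standard deviation, effect size or precision target for this substudy, so there is no figure to reproduce. The check has three parts.

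**1. Who can be on hormones at the baseline scan?** Assignment, scan and first insertion attempt normally share a day, so the switching rules for insertion also govern the scan.

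| Method at entry | State at the scan under Protocol 6.3 |
|---|---|
| Pill, patch, ring | Method continues past insertion; hormone-free week preferred where feasible |
| Monthly combined injection | Up to 28 days since last dose |
| Implant, hormonal IUS | Removed that day |
| Copper IUD | No hormone; any cycle day |
| Other non-hormonal | No hormone; cycle days 1 to 7 |

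The first three rows can enter. The exclusion in Protocol 4.3 concerns hormonal contraception used for cycle control, not for contraception. Depot medroxyprogesterone users are excluded for 9 months (6 with normal cycles). Nothing in 4.4.2 or SAP 11.14 removes or separates the first three rows.

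**2. How far could the pooled mean move?** Let p be the share of women on, or that day coming off, a hormonal method, and d the mean shift in their baseline due to that method. The pooled change is displaced by p × d. Both inputs are assumptions.

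| d (mm) | p = 0 | p = 25% | p = 50% | p = 75% |
|---|---|---|---|---|
| 1 | 0 | 0.25 | 0.50 | 0.75 |
| 2 | 0 | 0.50 | 1.00 | 1.50 |

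For scale, the 95% half-width of a mean change is 1.96 × SD/√n. With n = 60 it is 0.51 mm at an assumed SD of 2 mm and 1.01 mm at 4 mm. The displacement can therefore be negligible, or can equal or exceed the sampling error. The documents do not settle which.

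**3. How many women will be left?** Protocol 9.1 gives yearly discontinuation limits of 20%, 19%, 17% and then 16% for seven years, and a ten-year total of 76%.

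- Month 12: 60 × 0.80 = 48.
- Month 60: 60 × 0.80 × 0.81 × 0.83 × 0.84² = 22.8, about 23.
- Month 120, from the stated total: 60 × (1 − 0.76) = 14.4, about 14.
- Month 120, compounding the yearly limits: 60 × 0.80 × 0.81 × 0.83 × 0.84⁷ = 60 × 0.1587 = 9.5, about 10.

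These apply the main-study assumptions to the substudy. If half the remaining women were hormonal switchers (assumed), each row at Month 120 would hold about 5 to 7 women.

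**The case against.** The other side has several good points.

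- **Only some women are affected.** A reader might infer that every baseline is taken on hormones. The documents do not support that: entrants from non-hormonal methods are scanned off hormones.
- **There is partial mitigation.** Pill, patch and ring users are to be scheduled in the hormone-free week where feasible, and recent depot medroxyprogesterone users are excluded. This stands, but does not reach same-day implant or IUS switchers or recent monthly injections.
- **Some information is already planned.** SAP 7.3 summarizes baseline characteristics for the endometrial population, including recent menstrual history on and off hormones. SAP 11.14 reports absolute thickness, and the on-treatment values do not depend on baseline. Neither is crossed with the change, so the pooled change stays mixed.
- **Direction and time trend.** A reader might infer that the pooled change is pulled toward zero by a known amount, or that shifting prior-method mix will create a trend from Month 12 to Month 120. The documents do not say that earlier methods thin the endometrium, or by how much, and nothing in them shows that discontinuation differs by prior method. Both are possible, not shown.
- **A hormone-free subset as the main analysis.** This is tempting but not well supported. The 7-day criterion in 4.4.1 belongs to a plasma PK substudy and would class a woman 8 to 28 days after a monthly injection as hormone-free. The subset could be very small by Month 120. Copper-IUD users, scanned on any cycle day, would still make it heterogeneous.
- **Low stakes.** The outcome is descriptive, SAP 5.1 plans no formal testing, and no decision rule depends on it.

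**Conclusion.** The point holds in a limited form. The protocol allows hormone use at the baseline scan, and for pill, patch and ring switchers it directs that the method continue. The substudy has no hormone-free criterion and the SAP does not separate these women. With baseline as the only reference, the pooled change cannot be read cleanly as the change under LNG20 from an endometrium free of other hormones.

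The size is unknown. It is zero if no substudy woman was a hormonal switcher, and could match the sampling error under the assumed shares and shifts above. The conclusion rests on two things the documents leave open: that some of the 60 women were hormonal switchers, and that their earlier method affected the scan. The loss is in interpretability of one descriptive secondary outcome.

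**What to change.** Protocol 9.1 reports that assignment of subjects to this substudy is complete, so the remedy is in the analysis. In SAP 11.14:

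1. Keep the pooled summary as planned.
2. Add baseline thickness, absolute thickness and change from baseline at Months 12, 60 and 120, split by contraceptive status at the baseline scan (hormonal or non-hormonal), with n in each row.
3. Define hormonal as any of: a pill, patch or ring in current use; a monthly injection within the previous 28 days; an implant or hormonal IUS removed that day. All other women are non-hormonal.
4. Derive the variable from the contraception and medication history collected at screening (Protocol 6.3.1).
5. Specify this before data cut-off, since SAP 5.1 treats later additions as post hoc.

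The cost is one derived variable and a few lines of SAP text, with no new data collection. The drawback is small rows, above all at Month 120, where the split should be read as description only.
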